#### 14.3.2. Dose Expansion at Dose Level -2

As described in section 11.3.8, this protocol is amended to reduce the PVSRIPO dose to dose level -2 (1.0 X 10^7 TCID50) with the goal of limiting the occurrence of undesirable burden from the inflammation and its treatment on as many subjects (including caregivers) as possible. Based upon additional animal studies, we are confident that dose level -2 (1.0 X 10^7 TCID50) will be a therapeutic dose. This amendment is not due to concerns for the safety of the patients on dose level -1, but due to the observation that less inflammatory reaction is a predictor of better survival and treatment response.

Twenty-seven (27) patients will be accrued to the dose expansion at dose level -2. The ultimate goal of this accrual expansion is to determine whether PVSRIPO administered at dose level -2 has merit for further evaluation in additional clinical studies. The second historical control group as described in Appendix 18.4 and section 14.3.1 will be to make this assessment.

A false-positive rate of 0.2 will be used to test a hypothesis comparing dose level -2 with the historical control group while maintaining a high power level (e.g. 90%). The rationale is provided in section 14.3.1.

Given that recently reported studies of effective immunotherapeutic agents show (1) delayed antitumor effects and hence delayed separation of survival curves, and (2) a percentage of patients who are "cured" or survive for a relatively long period of time, we will focus on long-term survivorship at a specific time point (i.e. 24 months). Within the second historical control group, the 24-month survival probability is 13.5%. Assuming 27 patients in the historical group, simulation studies show that a two-tailed chi-square test ( $\alpha$ =0.2) conducted to compare the proportion of patients alive at 24 months at the 0.2 level has 88.7% power to detect an increase to 35% in 24-month survival. Logistic regression will be used to adjust for confounding factors.

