#### 11.3.11. Study Design Modification (3/1/2017 AMD124)

Based upon recent pre-clinical data and clinical data collected on dose levels -1 and -2, we have concluded that there is no evidence of pre-clinically or clinically important differences between these dose levels. The initial need for treatment with the radiation necrosis dose levels and schedules of bevacizumab for cerebral inflammation secondary to PVSRIPO or tumor growth has been comparable thus far. In addition, the toxicity

profiles for the two dose levels are also similar. Therefore, we have decided to proceed with the development of PVSRIPO dose level -1 (5.0 X 10^7 TCID50) within the phase II study that is now in development. We are amending this phase I study to treat all future patients at the -1 dose level. We intend to continue accruing patients and treating patients at this dose level while the phase II study is being finalized and reviewed by various regulatory bodies.

This protocol is also being modified to allow multiple patients to be infused with study drug simultaneously if the neuro-surgical schedule allows. There are currently 3 neurosurgeons listed as sub-investigators who are trained on the surgical procedures for this study. In the study modification dated 6/29/2016, the study was modified so that the next patient could be treated immediately following the completed infusion of the previous patient. However, we would like to increase our enrollment potential by allowing multiple patients to be treated simultaneously. As of 1/20/2017, no patients have experienced complications during the infusion of PVSRIPO. Only 1 out of 51 treated patients has experienced severe complications (Grade III or higher) during catheter removal following the infusion of the study drug, and therefore we are confident that treating multiple patients would be safe for the patients and would allow for increased data collection.

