#### 14.3. DOSE EXPANSION COHORTS

As described in section 11.3, the protocol amendment dated 6/24/2015 (AMD071) allowed the treatment of up to 50 subjects at dose level -1 to assess efficacy. The amendment dated 6/15/2016 (AMD096) reduced the PVSRIPO dose for treatment to dose level -2. Subsequently, amendment dated 2/9/2017 (AMD124) increased the treatment dose of PVSRIPO to dose level -1. Section 11.3 provides the rationale for all these changes.

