The ultimate goal of this accrual expansion and survival comparison is to determine whether PVSRIPO administered at dose level -1 and, as needed, with a radiation-necrosis dose level and schedule of bevacizumab in the manner described within this protocol has merit for further evaluation in additional clinical studies. This goal is analogous to that of a randomized phase II screening study, except for the fact that the two groups are not created by randomization. The second historical control group will be considered in this comparison. Typically, with a randomized phase II study, there is a need to constrain the sample size requirements at the expense of either an increased false negative or false positive rate. It has been recommended that a false-positive rate of 0.2 be used to test a hypothesis comparing arms while maintaining a high power level (e.g. 90%).

A total of 50 subjects will be accrued and treated at dose level -1. Assuming survival is exponentially distributed and the median survival associated with the -1 dose level is 15.2 months, we anticipate that approximately 15 of the 50 patients will be deceased by the time accrual is complete in June 2016. Without additional follow-up, the power of a logrank test conducted at the 0.2 level of significance (one-tailed) to detect a hazard ratio of 0.5, 0.55, 0.6, and 0.65 are 0.95, 0.91, 0.84, and 0.76, respectively. Tabulated below is the power to detect these hazard ratios as a function of the number of additional months of follow-up after accrual completion (Table 4).

Follow-	Expected # Dead if Median OS = 15.2 months	Power of Comparison to Detect Noted Hazard Ratio						
up (Months)		Hazard Ratio = 0.5	Hazard Ratio = 0.55	Hazard Ratio = 0.6	Hazard Ratio = 0.65			
0	15	0.95	0.91	0.84	0.76			
1	16	0.96	0.92	0.85	0.78			
2	18	0.97	0.93	0.88	0.80			
3	19	0.97	0.94	0.89	0.81			
4	21	0.98	0.95	0.90	0.83			
5	22	0.98	0.96	0.91	0.84			
6	23	0.98	0.96	0.91	0.85			
7	24	0.99	0.96	0.92	0.85			
8	26	0.99	0.97	0.93	0.87			
9	27	0.99	0.9	0.94	0.87			
10	28	0.99	0.97	0.94	0.88			
11	29	0.99	0.98	0.94	0.89			
12	30	0.99	0.98	0.95	0.89			

Table 4. Power of the survival comparison to detect the noted hazard ratios

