Given that the study is not a randomized study, there is a need to statistically adjust survival comparisons for confounding factors. Hence, survival comparisons will be conducted using the Cox model. Predictors within the Cox model will include treatment, age, extent of resection, prior bevacizumab treatment, Karnofsky performance status at the time of PVSRIPO treatment, number of prior recurrences, and an indicator of secondary GBM.

It should be noted that the calculations and analyses described above assume that survival with PVSRIPO is exponentially distribution and that the proportional hazards assumption is satisfied. Recently reported studies suggest that such properties may not exist for immunotherapeutic agents due to (1) delayed antitumor effects and hence delayed separation of survival curves, and (2) a percentage of patients who are "cured" or survive for a relatively long period of time. If that is the situation with PVSRIPO, the power calculations and planned analyses may not be appropriate. It might be more appropriate to focus on long-term survivorship at a specific time point such as 18 and 24-month survival. Within the second historical control group, the 18 and 24-month survival probabilities are 23.1% and 13.5%, respectively. A two-tailed chi-square test ( $\alpha$ =0.2) conducted to compare the proportion of patients alive at 18 or 24 months at the 0.2 level has >84% power to detect an increase of 15% in survivorship. Logistic regression will be used to adjust for confounding factors.

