A determination for the degree of monitoring conducted by the DCI monitoring team is made at the time of initial CPC approval to commensurate with the type and level of intervention, phase, endpoints, degree of risk, size and complexity of the protocol. Typically, a formal monitoring visit is conducted by the DCI monitoring team after the first 3 subjects have been enrolled, followed by annual monitoring of 1-3 subjects until closed to enrollment or subjects are no longer receiving study drug or other interventions that are more than minimal risk. In this study, beginning with the monitoring visit (MV) of September 2013, the DCI Monitoring Team has monitored the eligibility

of all subjects enrolled following completion of their 4-week follow-up. This monitoring of eligibility is in conjunction with annual monitoring of accrual, regulatory, consenting, eligibility, conduct, safety, data quality, investigation product accountability, and biologic samples. Additional monitoring may be prompted by findings from monitoring visits, unexpected frequency of serious and/or unexpected toxicities, or other concerns. Monitoring visits may also be initiated upon request by DUHS and DCI Leadership, CPC, SOC, a sponsor, an investigator, or the IRB. Following closure of enrollment to new subjects in June 2017, DCI monitoring will revert to standard monitoring practices (i.e. individual subject monitoring will be discontinued, while annual monitoring will continue while selected patients are being retreated).

The DCI monitoring team reviews the adequacy of informed consent, enrollment of appropriate patients, implementation of protocol-specified procedures and treatment, adequacy of data collection, and appropriateness of adverse event monitoring and reporting. The DCI monitoring team presents final monitoring reports to the DCI Safety Oversight Committee (SOC) highlighting safety concerns and unresolved issues. The SOC chair assigns an overall rating of satisfactory (no major deviations), marginal (1 major deviation), or unsatisfactory (2 or more major deviations or an ineligible subject) to reflect overall quality of data, regulatory, consent, eligibility, conduct and AE reporting. Corrective action plans (CAPs) are developed, implemented, and evaluated as indicated. The SOC will notify the Sponsor and DUHS IRB when significant safety concerns are identified.

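### Section 14.3.2 still plans 27 patients and 88.7% power at dose level -2, although AMD124 ended that cohort early; about 13 patients are implied, giving about 71% power.

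*Combined protocol and SAP*

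**What the plan says.** Section 14.3.2: "Twenty-seven (27) patients will be accrued to the dose expansion at dose level -2". The stated purpose is to decide whether level -2 merits further study. The comparison is of 24-month survival with the second historical control group (13.5% alive at 24 months; 104 patients according to section 14.3.1). It uses a two-tailed chi-square test at 0.2, which "has 88.7% power to detect an increase to 35% in 24-month survival".

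Section 14.3, which introduces that subsection, records that the "amendment dated 2/9/2017 (AMD124) increased the treatment dose of PVSRIPO to dose level -1". Section 11.3.11 gives the decision itself: "We are amending this phase I study to treat all future patients at the -1 dose level". Section 16.6 refers to the period "Following closure of enrollment to new subjects in June 2017".

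Section 14.3.1 still says "A total of 50 subjects will be accrued and treated at dose level -1" and expects accrual to finish in June 2016. Section 11.3.8 reports 23 patients treated at that level on 6/15/2016.

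Section 14.2 says that the secondary objectives will be assessed descriptively, warns that all dose levels are pooled, and says that no specific hypothesis will be tested.

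**The concern.** Section 14 was edited to record the return to level -1, but the sample size and power beneath that record were left alone. A reader of 14.3.2 would take the level -2 comparison to have an 11% chance of missing a true 24-month rate of 35%. If the cohort stopped at about half its planned size, that chance is well over twice as large.

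Section 14 also does not say what becomes of the level -2 test: whether it is run at the reduced size or falls back to the descriptive analysis of 14.2. Nor does it say whether level -1 patients treated before AMD096 and after AMD124 form one analysis set. What is at stake is how the level -2 survival result is read, and how clearly the analysis was fixed. The primary objective (MTD and phase II dose) is not affected.

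**Working it through.** **1. Reproduce the stated power.** Inputs from 14.3.1 and 14.3.2: p1 = 0.35, p0 = 0.135, difference 0.215, 104 controls, two-tailed 0.2 so z = 1.2816.

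Power ≈ Φ[(0.215 - 1.2816 × SE0) / SE1], where SE0 = √[p̄(1 - p̄)(1/n + 1/104)], p̄ is the weighted mean rate, and SE1 = √[0.35 × 0.65/n + 0.135 × 0.865/104].

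For n = 27: p̄ = (9.45 + 14.04)/131 = 0.1793; SE0 = 0.0829; SE1 = 0.0977; power = Φ(1.11) = 86.7%. Exact enumeration of the two binomials with an uncorrected chi-square gives 87.7%. Holding the controls fixed at 14/104 gives 88.5%. The stated 88.7% is therefore sound for 27 treated against 104 controls. Section 14.3.2 attributes the 27 to the historical group. This looks like a slip, because 27 against 27 gives only 71.9% (exact 73.5%).

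**2. Count the level -2 patients.**
- Treated by 6/15/2015: 28, of whom 13 at level -1 (14.3.1), leaving 15 at other levels.
- Treated at level -1 by 6/15/2016, when level -2 opened: 23 (11.3.8). Running total: 15 + 23 = 38.
- Treated in all by 1/20/2017: 51 (11.3.11). So 51 - 38 = 13 at level -2.

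The 13 would be slightly lower if anyone was still treated at level -1 after 6/15/2016. It would be slightly higher if level -2 treatment went on between 1/20/2017 and AMD124 (dated 2/9/2017 in 14.3 and 3/1/2017 in 11.3.11).

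For a generous figure, take the 59 subjects in the shedding report (11.3.13) as all treated subjects and place everyone after the first 38 at level -2: 59 - 38 = 21. On that assumption 27 was not reached, since 38 + 27 = 65 exceeds 59. Without it, reaching 27 would have needed 14 more level -2 patients in the roughly six weeks from 1/20 to 3/1/2017, against about 13 in the previous seven months.

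**3. Power at those sizes** (35% against 13.5%, 104 controls, two-tailed 0.2).

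| Level -2 n | Normal | Exact chi-square | Miss rate (exact) |
|---|---|---|---|
| 27 (planned) | 86.7% | 87.7% | 12% |
| 21 (generous) | 81.9% | 82.6% | 17% |
| 13 (derived) | 71.4% | 71.1% | 29% |

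For n = 13: p̄ = (4.55 + 14.04)/117 = 0.1589; SE0 = 0.1075; SE1 = 0.1365; (0.215 - 0.1378)/0.1365 = 0.57; Φ = 71.4%. With 13 patients, about 89% power needs a true 24-month rate of about 45%, not 35%.

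**4. What a result could look like.** With 3 of 13 alive at 24 months (23.1%) against 14/104: pooled rate 17/117 = 0.1453, z = 0.93, p = 0.35, not significant at 0.2. The exact 95% CI is 5% to 54%, which includes the 35% target. With 4 of 13, p = 0.10, significant at 0.2.

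**5. Level -1.** By 6/15/2016, the month in which 14.3.1 expected accrual to be complete, 23 of the planned 50 had been treated. On the same assumption about the 59, at most 59 - 51 = 8 more followed after 1/20/2017, making 31. The number is not stated, so I put no revised power on the 14.3.1 comparison.

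**The case against.** The strongest reply is that 14.3.2 records the design as set by AMD096, that 14.3 tells the reader the dose later changed, and that 14.2 supplies a descriptive, all-levels default. Planning power is also prospective: once accrual has stopped, the confidence interval carries the information. Part of this stands. Section 14 is not silent about a descriptive or pooled analysis, and the stated power was right when written. But 14.3.2 is current text in the future tense with a formal test and a false-positive rate, 14.2 says no hypothesis will be tested, and nothing says which governs level -2 now.

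Five stronger readings are tempting, and the documents do not support them:

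- **That 83% is a ceiling.** The 59 are subjects from whom stool was collected. Patients who gave no sample, or were treated too late for a report dated 8/6/2017, would not be counted.
- **That AMD124 was unsound because the 24-month test had not been done.** AMD124 rests on pre-clinical data, toxicity, and a need for "bevacizumab for cerebral inflammation secondary to PVSRIPO or tumor growth has been comparable thus far". It does not claim support from the 24-month test, and the primary objective is dose selection.
- **That a level -2 null would favour level -1.** The 14.3.2 test compares level -2 with historical controls, not with level -1, and level -1 had already been chosen for phase II.
- **That every analysis could still be fixed before outcomes were known.** Twelve level -1 patients were more than 12 months from treatment on 6/15/2016, with survival times and deaths already reported in 11.3.8. They had passed the 24-month point by June 2017, before the 9/25/2017 amendment. For level -2, no one could be confirmed alive at 24 months before June 2018, but any earlier death already settled that patient's status.
- **That pooling levels -1 and -2 is wrong.** Pooling is a legitimate choice. The need is to state it and say when it was made.

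**Conclusion.** The point holds as a stale size and power in current section 14. Power for the level -2 comparison is about 71% at the derived 13 patients, and about 83% at 21, against 88.7% stated. The 13 rests on subtracting counts reported at different dates; the 21 rests on reading the shedding report as covering all treated subjects. Either way, power falls below both the stated figure and the 90% that 14.3.2 gives as its example of a high level. The 50 in 14.3.1 is out of date in the same way, and 14.2 and 14.3 disagree on whether anything is tested. This should be corrected because it changes how a non-significant level -2 result is read. It does not undermine the dose decision or the safety objective.

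**What to change.** In 14.3.2, replace the sample-size text with wording such as:

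> AMD124 closed this cohort after [n] of the planned 27 patients. Power for 35% against 13.5% at 24 months is [computed from n; about 71% if n = 13]. The comparison with the second historical control group will be [carried out as a two-tailed chi-square test at 0.2 / descriptive, as in section 14.2]. The 24-month rate will be reported with an exact 95% CI. A non-significant result at this size does not show that level -2 lacks merit.

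In 14.3.1, replace 50 with the number treated at level -1, say that it covers patients treated before AMD096 and after AMD124, and restate the power. In 14.2, say which comparisons in 14.3 are exceptions to the no-testing statement. Label any pooled -1/-2 analysis as specified after some 24-month outcomes were known.

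The cost is one amendment to section 14, with no new patients or data. The downside is a lower stated power and a softer reading of the level -2 result.

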#### 14.3.1. Dose Expansion at Dose Level "-1"

Accrual at dose level -1 will be extended in order that a sufficient number of patients will be treated at that dose level to estimate its efficacy relative to a historical cohort.

As of 6/15/2015, 28 patients have been treated on this protocol, including 13 patients treated at dose level -1. The median survival is 15.2 months (95% confidence interval: 7,  $\infty$ ). Median follow-up among patients treated at dose level -1 is 3.5 months.

Informal comparisons of survival associated with PVSRIPO (including all patients at all dose levels) relative to that observed in other recurrent WHO grade IV malignant glioma patient groups suggest a hazard ratio in the ballpark of 0.5 to 0.65.

The historical cohort that will be used for this comparison will include recurrent WHO grade IV malignant glioma patients in the PRoGREss registry (IRB# Pro00027120; Primary and Recurrent Glioma Registry) who would have been eligible to receive PVSRIPO if the treatment had been available. Details about the construction of this comparison group, as well as a summary of control group patient characteristics are provided in Appendix 18.4. Two control groups were generated, with one group having no limit to pre-treatment steroid usage, and the other group having a steroid limit of  $\leq$  4 mg per day of dexamethasone within the 2 weeks prior to being eligible for PVSRIPO infusion. The first control group has eligibility criteria similar to that which was in existence for dose levels 1-5 and the first 5 patients on dose level "-1". The second control group has eligibility criteria similar to those currently being used for dose level "-1". The first historical control group includes 124 patients of which 123 are dead; whereas, the second historical control group includes 104 patients of which 103 are dead.

Korn and Friedlin (48) recommend the use of an unconditional power estimator for the determination of sample size in single arm studies that compare time-to-event outcomes such as survival with that observed in a historical control group. That estimator resembles an estimator for a 2-arm randomized study. The power of such a comparison is dependent upon the total number of observed deaths (49).

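### The adjusted 24-month survival model at dose level -2 names no covariates or estimator; with the Cox covariates and maximum likelihood, the odds ratio would be about 9–16% too high at the design effect

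*Combined protocol and SAP*

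**What the plan says.** Section 14.3.2 sets the size of the expansion ("Twenty-seven (27) patients will be accrued to the dose expansion at dose level -2") and its endpoint ("we will focus on long-term survivorship at a specific time point (i.e. 24 months"). The benchmark comes from the registry controls: "Within the second historical control group, the 24-month survival probability is 13.5" per cent. Section 14.3.1 gives the size of that group: "the second historical control group includes 104 patients of which 103 are dead".

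The test is a two-tailed chi-square. On its error rate the section says "A false-positive rate of 0.2 will be used to test a hypothesis comparing dose level -2 with the historical control group", and it states that the test "has 88.7% power to detect an increase to 35% in 24-month survival".

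Adjustment gets one sentence: "Logistic regression will be used to adjust for confounding factors". No covariates are listed for this model, no estimator is named, and nothing is said about a fit that fails to converge. The only confounder list is in Section 14.3.1, for a different model: "Predictors within the Cox model will include treatment, age, extent of resection, prior bevacizumab treatment", followed by Karnofsky status, number of prior recurrences and secondary GBM. That is treatment plus six covariates.

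**The concern.** The controls are not randomised, and Section 14.3.1 gives that as the reason survival comparisons must be adjusted. The adjusted odds ratio is therefore the estimate a reader will look to. Maximum-likelihood logistic regression with few events per coefficient gives log odds ratios biased away from zero. If a covariate group contains no survivors, its coefficient runs to infinity. With only about 14 survivors among the controls and some thin groups (11 of 104 controls have secondary GBM), both problems can be expected.

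Because the plan has no rule for this, an analyst whose fit fails would have to drop a covariate, merge levels or change method after seeing the outcomes. Section 16.6 sets up a DSMB-Plus because of an institutional conflict of interest, so this is a freedom worth closing in advance.

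**Working it through.** **The plan's own figure.** Inputs from 14.3.1 and 14.3.2: 13.5% against 35%, two-sided alpha 0.2, stated power 88.7%. Taking 27 treated against 104 controls, power is 0.867 by the normal approximation, 0.877 by exact enumeration of the uncorrected chi-square, and 0.885 with controls fixed at 14 of 104. The figure reproduces. The section attaches the 27 to the historical group; read literally as 27 against 27, power is only 0.72 to 0.73, so 27 must be the treated group.

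**Survivors per predictor** (survivors = 104 × 0.135 + 27 × p; 104 × 0.135 = 14.04).
- Design effect, p = 0.35: 14.04 + 9.45 = 23.5. Divided by 7 predictors this is 3.4; by 8 coefficients (resection in three levels), 2.9.
- No effect, p = 0.135: 14.04 + 3.65 = 17.7. Divided by 7 this is 2.5; by 8, 2.2.

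**Bias at the design effect.** Simulated trials of 27 against 104, 3,000 to 4,000 per scenario. Covariate frequencies come from Appendix 18.4, with the same mix in both groups. Covariate effects are assumed at three strengths, because the documents give none. Mean odds ratios are exponentiated mean log odds ratios, and ranges cover 7 and 8 coefficients.

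| Assumed covariate effects | True OR | Maximum likelihood | Excess | Firth |
|---|---|---|---|---|
| None | 3.45 | 3.75–3.88 | 9–12% | 3.42–3.47 |
| Moderate | 3.56–3.57 | 3.95–4.02 | 11–13% | 3.57 |
| Strong | 3.92 | 4.40–4.54 | 12–16% | 3.89–3.93 |

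With no treatment effect the maximum-likelihood mean is 0.92–0.97, so there is no upward bias.

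**Failed fits.** Some coefficient diverges in 6–12% of trials at the design effect and in 17–29% with no effect. The usual culprits are secondary GBM, resection type and prior recurrences. All but 1 of 36,000 Firth fits converged.

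**When treatment itself diverges.** This happens mainly when no treated patient survives, with probability (1 − p)^n.
- n = 27: 0.65^27 is about 0 at the design effect; 0.865^27 = 0.02 with no effect.
- n = 13: 0.65^13 = 0.004 at the design effect; 0.865^13 = 0.15 with no effect.

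**Where 13 comes from.** By 6/15/2015, 28 patients had been treated, 13 of them at level -1 (14.3.1), so 28 − 13 = 15 were at other levels. By 6/15/2016, 23 had been treated at level -1 (11.3.8), giving 15 + 23 = 38 in all. By 1/20/2017, 51 had been treated (11.3.11), and 51 − 38 = 13. This assumes that everyone treated between the last two dates received level -2 and that none followed before the return to level -1. With 13 treated, some coefficient diverged in 16–17% of simulated trials at the design effect and in 34–35% with no effect.

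**Precision.** Across simulations with different assumed covariate effects, the root-mean-square error of the log odds ratio at the design effect was 0.62–0.68 for maximum likelihood and 0.54–0.57 for Firth with 27 treated. With 13 treated it was 0.89–0.95 and 0.73–0.74.

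**Error rates.** With 27 treated, the adjusted Wald test rejects in 0.18–0.19 of trials with no effect (nominal 0.20) and in 0.86–0.88 at the design effect. Firth power is also about 0.86–0.88.

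**The case against.** The strongest reply is that the plan has not chosen badly; it has left the model open. The seven predictors are listed for the Cox model only, and unqualified logistic regression does not exclude a penalised fit. A model with treatment, age, prior bevacizumab and Karnofsky status cuts the excess to about 4–5% and failures at the design effect to about zero. So listing fewer covariates would remove most of the problem without Firth. This stands, and it is why the size above is conditional. It also confirms that the covariates need naming.

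The bias is also small beside the sampling error: about 0.14 on the log scale against a root-mean-square error of 0.63, or 0.14/0.63 = 22%. That stands too.

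Several stronger readings are tempting, and the documents do not support them.
- **An ineffective dose would look effective.** The mean odds ratio with no effect is below 1, and the false-positive rate is not inflated.
- **The treatment estimate would often be lost.** With 27 treated, the coefficient that diverges is almost always a covariate. With 13 and no effect treatment does diverge in about 15% of trials, but towards zero, not upward.
- **Only about 13 patients were treated at level -2.** The documents do not say so; it is an inference from three dated counts.
- **Seven controls with three progressions form a sparse cell.** They do so only if recurrences enter as categories; the 14.3.1 list refers to their number, which can be a single term.
- **Dose level -1 is equally affected.** Section 14.3.1 plans 50 treated and offers milestone survival only as a fallback. Simulated bias there is about 0.06–0.08 on the log scale, with divergence of about 0.6% at 18 months and 3% at 24 months.

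**Conclusion.** The point holds as a cheap improvement to the adjusted analysis in Section 14.3.2. It is not a flaw in the test or in the decision about dose level -2. If the Cox predictors are used with maximum likelihood, there are about 3.4 survivors per predictor at the design effect and 2.5 with no effect. The adjusted odds ratio is then roughly 9–16% too high at the design effect, and some coefficient diverges in about 6–12% of trials (17–29% with no effect).

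This rests on three assumptions: that the Cox list carries over, that unqualified logistic regression means maximum likelihood, and that the assumed covariate effects and equal covariate mix are reasonable. The upward bias does not depend on the assumed effects, since it appears with none. If far fewer than 27 were treated, stability worsens.

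**What to change.** In Section 14.3.2, list the covariates and their coding, and state that the adjusted 24-month model will be fitted by Firth penalised logistic regression with profile-likelihood intervals. Using the same method for the fallback milestone analysis in Section 14.3.1 is optional, because the problem is milder with 50 treated.

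The cost is a line in the plan and standard software. The downside is slight shrinkage of the estimate; simulated power is unchanged.
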